#### **1.3.2 Treatment of recent HCV infection in PWID**

While the majority of HCV transmission in the developed world occurs in the setting of IDU, there are limited data on treatment of acute HCV infection in PWID. In a small Swiss study, 22 patients with acute HCV were assessed for treatment and 14 commenced PEG-IFN alfa-2b for 24 weeks (58). By ITT, the SVR 24 was 57%. However, adherence was poor with only 8 patients completing more than 80% of the scheduled treatment

course (SVR by per-protocol analysis, 88% [7/8]). De Rosa et al offered 12 weeks of directly observed therapy with PEG-IFN alfa-2b with a much improved SVR 24 of 74% (17/23) (59). Adherence was excellent with 96% (22/23) completing more than 80% of the scheduled treatment course.

The largest trial to date examining treatment of acute and early chronic HCV infection involving PWID was ATAHc, a multicentre prospective cohort study of the natural history and outcomes following treatment with PEG-IFN alfa-2a with or without RBV (60). Between 2004 and 2008, 167 subjects were enrolled, of whom 111 (76%) with detectable HCV RNA at screening elected to commence treatment. 57% of the treated population were GT 1, 85% had acquired HCV via IDU and the median estimated duration of infection was 25 weeks. 33% of subjects were HIV co-infected (predominantly sexual [per mucosal] transmission). In the cohort of 74 HCV mono-infected individuals who commenced PEG-IFN monotherapy, the SVR 24 by ITT and per protocol analyses were 55% and 72%, respectively, with 77% (57/74) receiving at least 80% of the scheduled treatment course. While the SVR rate was lower in those who had a history of IDU (history of IDU, SVR 24 48% vs no IDU, SVR 24 91%,  $p = 0.03$ ), after adjusted analysis, the only pre-treatment factors associated with treatment failure were poor social functioning and a history of drug dependency treatment.

Collectively, these data demonstrate that PWID with recent HCV infection can be treated successfully, but that strategies to optimize adherence in socially marginalized populations are required to improve outcomes.

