### 11.3 Analyses

Efficacy analyses:

There will be one primary pair-wise comparison of the efficacy endpoints: shortened duration therapy versus standard duration therapy. Comparisons will be simple, direct two-sample comparisons of randomised treatment groups unadjusted for baseline covariates. If there is evidence of substantial imbalance at baseline in important covariates, further adjusted analyses will also be performed. If any randomisation mistakes occur, such that patients incorrectly receive the wrong treatment, then key efficacy endpoints will be performed where these patients will be excluded.

The primary analysis will compare randomised treatment groups on an ITT basis including all available data. The primary endpoint, SVR12, will be calculated for each patient based on all available data. Treatment arms will be regarded as non-inferior if the difference in proportion between regimens has a lower limit greater than -12%. Secondary analyses will compare randomised treatment groups based on available data (per protocol).

Proportions and 95% confidence intervals will be reported for both the primary and secondary virological endpoints. These will be provided overall, by treatment duration, by HCV genotype and by HIV status, and will be assessed for both the ITT and PP populations.

SVR 4, SVR 12 and SVR 24 rates will be compared to SVR rates demonstrated in historical controls in the ATAHc I, ATAHc II, DARE-C I and DARE-C II studies. Differences in proportions between studies will be summarised as n (%) in each group, with percent difference between cohorts with 95% confidence interval.

Factors associated with ITT study population treatment efficacy will be evaluated by univariate analysis, and will include, but are not limited to, the following variables: socio-demographic factors (age, gender, ethnicity); virological factors (baseline HCV viral load, HCV genotype); risk behaviors (injecting drug use, sexual behaviour); and HIV co-infection.

Additional treatment efficacy evaluations will be conducted among the *per protocol study population*, defined as subjects who receive >80% of planned treatment.

The impact of 80/80 adherence, 90/90 adherence, 100/100 adherence, on-treatment adherence and early discontinuation on SVR will also be evaluated.

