The modified Intention to Treat (mITT) population includes participants in the FAS excluding those with non-virological reasons for treatment failure (i.e., death, loss to follow up) and reinfection. Participants with confirmed reinfection after achieving an ETR, but prior to the primary efficacy endpoint (SVR12), will be excluded from the mITT.

Per-protocol Analysis Set

The PP population is defined as all participants who received >90% of scheduled treatment for >90% of the scheduled treatment period with follow-up virologic data to SVR12.

Safety Population

The Safety population includes all participants who randomised and will be analysed and presented according to the actual on-treatment monitoring arm received during the study.

The ITT population will be used for primary efficacy analyses, and the safety population will be used for all safety analyses.

Data Handling Conventions

Missing Data

For the analyses of categorical HCV RNA data, missing post-treatment HCV RNA data will have the missing data imputed. Missing on-treatment HCV RNA will have the missing data imputed up to the time of the last dose.

If a data point is missing and is preceded and followed in time by values that are "<LLOQ, TND," then the missing data point will be set to "<LLOQ, TND."

If a data point is missing, and preceded and followed by values that are "<LLOQ, target detected," or preceded by "<LLOQ, target detected" and followed by "<LLOQ, TND," or preceded by "<LLOQ, TND" and followed by "<LLOQ, target detected," then the missing value will be set to "<LLOQ, target detected."

If a data point is missing, and preceded and followed by values that are ">LLOQ, target detected," or preceded by ">LLOQ, detected" and followed by "<LLOQ, target detected" or "<LLOQ, TND", then the missing value will be set to ">LLOQ, target detected."

The following scenarios describe a framework for analysis of the primary endpoint based on various anticipated events for the ITT and mITT population:

- i. In the event of the participant dying or becoming lost to follow-up prior to SVR 12, the participant will be considered to have failed treatment (loss to follow up = failure)
- ii. If the SVR 12 time-point measure is missing, then the next available measure (i.e., SVR 24 or later) will be used. If no future time points are available, the participant will be considered a treatment failure.

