	To evaluate patient interest and attitudes towards long acting parenteral hepatitis C therapy (Long-Acting Hepatitis C Therapy Questionnaire)	Not included in primary analysis	

Primary efficacy endpoint

The proportion of participants with HCV RNA below the level of quantitation (target not detected [TND] or target detected, not quantifiable [TDnq]) at 12 weeks post end of treatment (SVR12)

The primary analysis will compare randomised treatment groups on an ITT basis including all available data. The primary endpoint, SVR12, will be calculated for each patient based on all available data. Treatment arms will be regarded as non-inferior if the difference in proportion between regimens has a lower limit greater than -12%. Secondary analyses will compare randomised treatment groups based on available data (per protocol).

Secondary efficacy endpoints

- Virological endpoints
 - The proportion of treated participants with:
 - ETR (defined as undetectable plasma HCV RNA at the end of treatment)
 - SVR4 (defined as undetectable plasma HCV RNA at post-treatment week 4)

For virological endpoints, the point estimates and 95% exact confidence intervals will be reported by study arm, by HCV genotype and by HIV serostatus.

Virological endpoints (Table 13 and 14)

The presence of HCV RNA will be assessed at all scheduled clinic study visits using Aptima HCV Quant Dx assay, version 2.15.5 (lower limit of quantitation [LLOQ] 10IU/mL; Hologic, Inc., Marlborough, MA, USA), with centralised testing performed at St Vincent's Centre for Applied Medical Research (Sydney, NSW, Australia).

Proportions and 95% confidence intervals will be reported for both the primary and secondary virological endpoints. Virological endpoints will be assessed in the ITT, mITT and PP populations, with results stratified by HCV genotype/subtype and HIV serostatus.

Factors associated with treatment outcome in the ITT population will be evaluated by univariate analysis. Variables assessed will include but are not limited to: demographic factors (age, gender); virological factors (baseline HCV RNA, genotype 1 subtype, duration of HCV infection); risk behaviors (injecting drug use, sexual behavior, mode of HCV acquisition); HIV co-infection; treatment factors (adherence).

Primary safety endpoints

The primary safety endpoints are:

- Proportion of participants with common adverse events (reported by greater than 5% of the study population);

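### The factor analysis is univariate in ITT only and does not list treatment arm, so behaviour effects can partly reflect loss or reinfection, and an adherence effect can be masked

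*SAP*

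**What the plan says.** Protocol 11.3 states: "Factors associated with ITT study population treatment efficacy will be evaluated by univariate analysis". It adds a second analysis with no analysis set or model named: "The impact of 80/80 adherence, 90/90 adherence, 100/100 adherence, on-treatment adherence and early discontinuation on SVR will also be evaluated". The SAP, under Virological endpoints, repeats the first plan: "Factors associated with treatment outcome in the ITT population will be evaluated by univariate analysis". Its open-ended list of variables includes "risk behaviors (injecting drug use, sexual behavior, mode of HCV acquisition); HIV co-infection; treatment factors (adherence"). Arm is not on the list, and no multivariable model is planned.

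The ITT outcome is set under Missing Data in the SAP. After death or loss before SVR12, "the participant will be considered to have failed treatment (loss to follow up = failure"). A second rule softens this: "If the SVR 12 time-point measure is missing, then the next available measure (i.e., SVR 24 or later) will be used". Only if no later value exists is the result a failure. Reinfection is dealt with in one place: "Participants with confirmed reinfection after achieving an ETR, but prior to the primary efficacy endpoint (SVR12), will be excluded from the mITT". It follows that reinfection before SVR12 stays a non-SVR12 in ITT, and SAP Table 13 lists it under SVR12 beside non-response, relapse and loss.

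The mITT and PP sets are used for the virological endpoints themselves. Neither is named for the factor analysis. SAP Table 12 makes that analysis an additional outcome, to be run only if SVR12 is low. The DSMB section of the SAP reports that the short arm was stopped for inferiority.

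**The concern.** The outcome mixes antiviral failure with retention and re-exposure. Injecting and sexual behaviour are routes to reinfection and may also go with loss to follow-up. A univariate ITT result for these factors cannot tell a drug that works less well from a person who left or was infected again. The Protocol nevertheless calls the target treatment efficacy, and SAP Table 12 calls it on-treatment efficacy.

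Arm raises a separate problem. It predicts outcome, and it also affects how likely a participant is to take every dose, because the courses differ in length. A crude adherence comparison across both arms is therefore confounded by arm.

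Secondary objective 3 asks how suboptimal adherence affects response. With one arm stopped, readers will also ask who fails the short course. A behaviour effect that is really loss or reinfection could mislead about the very people the trial is meant to serve.

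**Working it through.** The plan gives no figure for this analysis, so there is none to reproduce. The sample size of 113 per arm plays no part here.

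**Inputs from the documents.** Reinfection of 4.7 per 100 person-years overall and 7.3 with ongoing injecting, with 38% still injecting (Protocol 1.3.6, an earlier cohort). Analysis set of 192: 93 short, 99 standard (SAP). Once-daily dosing, so 42 or 84 doses.

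**Assumptions.** Virological failure V is equal in both behaviour groups, at 4% or 10%. Losses L, arm-specific SVR and the rate of missed doses are also assumed.

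**1. Reinfection by 12 weeks.** Treating 38% as the share of person-time, the rate in the others is (4.7 − 0.38 × 7.3)/0.62 = 3.1 per 100 person-years. Twelve weeks is 0.230 years. The risks are 1 − exp(−0.073 × 0.230) = 1.7% and 1 − exp(−0.031 × 0.230) = 0.7%.

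**2. Apparent effect of injecting when it has no virological effect.** Non-SVR12 = 1 − (1 − V)(1 − L)(1 − R), where R is the reinfection risk. The last column is the share of 20,000 simulated comparisons (73 injecting v 119 not, as 38% of 192 is 73) with two-sided p<0.05.

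| V | Loss, injecting v other | Non-SVR12 | Odds ratio | p<0.05 |
|---|---|---|---|---|
| 4% | 0% v 0% | 5.6% v 4.7% | 1.21 | 5% |
| 4% | 5% v 5% | 10.3% v 9.4% | 1.10 | 5% |
| 4% | 5% v 2% | 10.3% v 6.6% | 1.63 | 16% |
| 4% | 10% v 5% | 15.0% v 9.4% | 1.70 | 22% |
| 4% | 10% v 2% | 15.0% v 6.6% | 2.51 | 48% |
| 10% | 0% v 0% | 11.5% v 10.6% | 1.09 | 5% |
| 10% | 5% v 5% | 15.9% v 15.1% | 1.06 | 6% |
| 10% | 5% v 2% | 15.9% v 12.4% | 1.33 | 11% |
| 10% | 10% v 5% | 20.3% v 15.1% | 1.44 | 16% |
| 10% | 10% v 2% | 20.3% v 12.4% | 1.80 | 32% |

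Example (last row): 1 − 0.90 × 0.90 × 0.9834 = 0.2035 and 1 − 0.90 × 0.98 × 0.9929 = 0.1243, so the odds ratio is (0.2035/0.7965)/(0.1243/0.8757) = 1.80.

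**3. Arm omitted, baseline factor.** Arm is randomised, so a null factor stays at 1.00. Take assumed failure of 22% (short) and 10% (standard), and a factor with odds ratio 2 within each arm. Failure with the factor is then 36.1% and 18.2%. Weighted 93:99, the totals are 26.8% with the factor v 15.8% without, an odds ratio of 1.95. With arm failure of 20% and 3% it is 1.87. A true effect shrinks slightly.

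**4. Arm omitted, adherence.** Assume a 1% chance of missing each daily dose, arm SVR of 80% (short) and 90% (standard), and no effect of adherence.

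- Full adherence: 0.99^42 = 65.6% (short) and 0.99^84 = 43.0% (standard), or 61.0 of 93 and 42.6 of 99 participants.
- SVR in the fully adherent: (61.0 × 0.80 + 42.6 × 0.90)/103.5 = 84.1%.
- SVR in the rest: (32.0 × 0.80 + 56.4 × 0.90)/88.5 = 86.4%.

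Those who miss doses look 2.3 points better although adherence does nothing. With assumed non-adherence of 10% v 20%, 20% v 40% or 30% v 50% (short v standard) and failure of 22% v 10%, the crude odds ratio of failure for non-adherence is 0.80 to 0.83.

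**The case against.** A reader might infer that risk behaviour and non-adherence are made to look like drug failure by construction. The documents do not support that.

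- Reinfection alone moves the result little, and false positives stay near 5%. Anything larger needs losses that differ by behaviour, and the documents give no such figure. The next-available-value rule also reduces the number of losses counted as failures.
- Omitting arm leaves a null baseline factor null. For adherence it works the other way and makes missed doses look harmless.
- Participants lost on treatment would count as both non-adherent and failed, but the SAP says the 192 completed their randomised treatment. Randomisation falls between weeks 5 and 6, so earlier losses never enter ITT. A short-arm participant lost after week 5 could still have 35/42 = 83% of doses. Poor adherence can also truly cause relapse.

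The plan has other defences. SAP Table 13 separates the types of failure, Tables 16 and 17 give reinfection and relapse by arm, and a later SAP table lists each virological failure with adherence. Factors for reinfection are a separate analysis. The SAP sentence says outcome rather than efficacy, and the variable list is open, so arm could be added. Protocol 11.3 promises further efficacy evaluations in the per-protocol set.

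These points limit the concern but do not remove it. Descriptive splits by arm do not estimate a factor's association with virological failure. The per-protocol sentence does not mention factors. An open list permits arm but does not require it, and a univariate analysis cannot adjust for it.

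Protocol 1.3.2 is weak support either way. Injecting history went with lower SVR (48% v 91%), yet "after adjusted analysis, the only pre-treatment factors associated with treatment failure were poor social functioning and a history of drug dependency treatment". That was interferon, and drug dependency treatment may stand in for injecting.

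**Conclusion.** The point holds in a limited form. As written, the factor analysis cannot separate antiviral failure from loss or reinfection, and nothing in it accounts for arm.

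For injecting, the distortion is an odds ratio of about 1.06 to 1.21 from reinfection alone. This uses the point estimates in Protocol 1.3.6, whose intervals are wide (1.9 to 11.2 overall and 2.3 to 22.6 with ongoing injecting). It rises to about 1.3 to 2.5 only under the assumed differential losses. The documents give no reinfection rate by sexual behaviour, so that effect is not sized.

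For arm, the harm is modest attenuation of true baseline effects and possible masking or reversal of an adherence effect. The latter assumes that doses are missed more often over the longer course and that the short arm has the lower SVR. The stop for inferiority makes the second assumption reasonable.

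The analysis is secondary and conditional on a low SVR12, although the stopped arm makes that condition likely to be met. The primary comparison does not depend on it.

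**What to change.** - Keep the ITT factor analysis, labelled as factors for overall non-SVR12.
- Repeat it in the mITT set with virological failure (non-response, breakthrough, relapse) against SVR12 as the outcome. Write that outcome out in full: the SAP's Study Definitions limit virologic failure to non-response, while Table 13 also includes breakthrough and relapse.
- State that deaths and losses are excluded from this version. The mITT definition excludes them, but the Missing Data scenarios apply the loss-as-failure rule to mITT as well.
- Include arm as a covariate in every factor and adherence model, including the adherence analyses of Protocol 11.3.

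The cost is SAP wording and a few models on data already collected. There will be few events, so estimates will be imprecise. The mITT version conditions on retention after randomisation and can bring selection bias of its own, so the two versions should be read side by side. The SAP counts recurrence by SVR12 as relapse unless reinfection is confirmed, so some reinfections may remain among the virological failures. A larger multivariable model is a matter of preference and is not needed to meet this point.

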***relapse definition:**

Analysis tables will also be presented for the mITT, and PP populations

Table 14. SVR12 in participant subgroups, ITT population

Subgroup	Standard tx arm n/N (%; 95% CI)	Shortened tx arm n/N (%; 95% CI)
HCV mono-infection		
HIV/HCV co-infection		
Genotype 1		
Genotype 1a		
Genotype 1b		
Genotype 2		
Genotype 3		
Genotype 4		
Genotype 5		
Genotype 6		

Other secondary outcomes

Table 15: Primary reason for premature discontinuation of study drug

Reason for premature discontinuation, n (%)	Standard tx arm (n=XXX)	Shortened tx arm (n=XXX)
Adverse event		
Non-compliance		
Withdrawal of consent		
Loss to follow up		
Other Specify - list		

Table 16: Reinfection by SVR12

	N	%	95% CI
Standard Arm			
Shortened Arm			

Table 17: Relapse by SVR12

	N	%	95% CI
Standard Arm			
Shortened Arm			

Table 18. Prevalence of polymorphisms in NS5B and NS5A at baseline

Polymorphism, n (%)	Total study population N=XXX	Standard duration arm N=XXX	Shortened duration arm N=XXX
Any NS5B	N	N	N
[Specify]			
Any NS5A	N	N	N
M28G/S/T			
L31F/I/M/P/V			
P32A/L/Q/R			
A/C92K/T			
Y93D/H/N/R/S/W			

Baseline polymorphisms detected by Sanger sequencing at the following amino acid positions:

NS5A: 28, 31, 32, 92, 93

Table 19. NS5B and NS5A polymorphisms at baseline and virologic failure

Subject ID	Genotype and subtype	Virologic failure	NS5B Variants		NS5A variants	
			Baseline	Failure	Baseline	Failure
Standard treatment duration (12 weeks), n=XXX						
Shortened treatment duration (6 weeks), n=XXX						

Table 19. Characteristics of participants with virological failure

Subject ID	Genotype and subtype	Virologic failure	Genetic distance % ¹		Baseline HCV RNA (log ₁₀)	Adherent ²
			Core-E2 ¹	NS5A		
Standard treatment duration (12 weeks), n=XXX						
Shortened treatment duration (6 weeks), n=XXX						

1. Reported genetic distance % for Core-E2 and NS5A was the comparison between sequences at baseline and post-treatment week 12. Cut-off for homologous virus was <4% for Core-E2 and X% for NS5A.

2. Adherence was defined as receipt of ≥95% of the prescribed treatment course

Table 21. On treatment adherence

	N	%	95% CI
80% adherence			
Standard Arm			
Shortened Arm			
90% adherence			
Standard Arm			
Shortened Arm			
100% adherence			
Standard Arm			
Shortened Arm			

SAFETY ANALYSES

All participants who receive at least one dose of study drug will be included in the safety analyses. Safety analyses will be performed overall and by treatment arm. Safety will be evaluated by assessment of clinical laboratory tests at various time points during the study, and by the documentation of AEs.

All safety data collected on or after the first dose of study drug administration up to 30 days after the last dose of study drug will be summarised.

Extent of Exposure

A participant's extent of exposure to study drug will be generated from the study drug administration page of the eCRF.

Adverse Events

Clinical and laboratory AEs will be coded using the Medical Dictionary for Regulatory Activities (MedDRA, [insert version](#)). System organ class (SOC), high level group term (HLGT), high level term (HLT), preferred term (PT), and lower level term (LLT) will be provided.

Events will be summarised on the basis of the date of onset for the event.

A treatment-emergent AE (TEAE) will be defined as:

- Any AEs with an onset date on or after the study drug start date and no later than 30 days after permanent discontinuation of study drug
- Any AEs leading to premature discontinuation of study drug

Adverse Event Severity

Adverse events are graded by the investigator as mild (Grade 1), moderate (Grade 2), severe (Grade 3), or life-threatening (Grade 4) according to toxicity criteria specified in the protocol. The severity grade of events for which the investigator did not record severity will be categorized as "missing" for tabular summaries and data listings, and the most severe will be considered (for sorting purpose only) in data presented. For example, if an adverse event of the same type (PT) is listed more than once for an individual, the highest grade will be used to summarise severity.

Relationship of Adverse Events to Study Drug

Related AEs are those for which the investigator selected "Related" ("Possibly related" or "Probably related") on the AE CRF to the question of "Related to Study Treatment." Events for which the investigator did not record the relationship to study drug will be considered to be related to study drug for summary purposes.

Summaries of Adverse Events and Deaths

The number and percentage of participants overall and in each arm with treatment-emergent adverse events will be tabulated by primary MedDRA System Organ Class (SOC) and preferred term (PT). The tabulation of the number of participants with treatment-emergent adverse events by severity grade and relationship to study drug also will be provided.

Participants reporting more than one adverse event for a given MedDRA PT will be counted only once for that term using the most severe grade for the severity grade table and the most related for

the relationship to study drug tables. Participants reporting more than one type of event within a SOC will be counted only once for that SOC, but both PTs will be listed.

Summaries of treatment-emergent AEs (by SOC and PT) will be provided for the following:

- All TEAEs
- TEAEs of Grade 3 or above
- All treatment-related TEAEs
- Treatment-related TEAEs of Grade 3 or above
- All SAEs (including death)
- All treatment-related SAEs
- All TEAEs leading to premature discontinuation of the study drug
- TEAEs that occurred in at least 5% of subjects within any treatment group

Adverse event summaries will provide the number and percentage of subjects with treatment-emergent AEs by SOC and PT, divided by treatment group.

Adverse events will be summarised and listed first in alphabetic order of SOC and then by PT in order of descending incidence of the pooled treatment groups within each SOC.

In summaries by severity grade, the most severe grade will be used for those AEs that occurred more than once in a participant during the study.

Serious adverse events (SAE)

The proportion of participants with at least one SAE will be reported overall. Serious adverse events will be summarized and relationship between the SAE and study drug will be detailed

Laboratory Evaluation

Selected laboratory data will be summarised (n, mean, SD, median, IQR, range) by study visit along with the corresponding change from Baseline/Day 1 to Post Treatment Week 12.

Depending on sample distribution, parametric or non-parametric tests can be used to compare the change in biochemical and haematological indicators over time.

The NIH DAIDS AE Grading Table Version 2.0- November 2014 will be used to grade severity.

Table 22. Safety parameters – adverse events and treatment discontinuation

Adverse events	Safety analysis set (N=XX)
Participants reporting any AE up to 30 days after last dose, n (%) Grades 1-2, n (%) Grade 3, n (%) Grade 4, n (%)	
Participants reporting treatment-related AE up to 30 days after last dose, n (%) Grades 1-2, n (%) Grade 3, n (%) Grade 4, n (%)	
Serious adverse event, n (%)	
Treatment-related serious adverse event, n (%)	
Treatment discontinuation due to adverse event, n (%)	
Death, n (%)	
Adverse events Common (>10% of study population), n (%) Specify (list)	

Table 23. Listing of serious adverse events

Study Arm	Date Onset	Date resolved	Diagnosis or event description	SAE criteria‡	Outcome§	Relationship to study drug
Standard						
Shortened						

‡ Death, hospitalised, life threatening, medically important, congenital anomaly, disability

§ Recovered, Improved, Unchanged, Worsened, Unknown, Died

Table 24. Serious adverse events summary

SAE – event summary	All N=XXX	Treatment arm 1 N=XXX	Treatment arm 2 N=XXX
N of participants experiencing any treatment-emergent SAE by MedDRA SOC and Preferred Term, n (%) SOC (alphabetical order) List PT			

Laboratory Evaluation

Selected laboratory data will be summarised (n, mean, SD, median, IQR, range) by study visit along with the corresponding change from Baseline/Day 1.

Table 25. Summary table for key laboratory evaluations

Lab parameter	N	Mean	SD	Min	Q1	Median	Q3	Max
ALT								
AST								
Glucose								
ALP								
Albumin								
Creatinine								
Haemoglobin								
WBC								
Neutrophils								
Platelets								
Bilirubin								

*table will be further stratified by Arm and study weeks (Screening, baseline, Week 4, ETR, SVR4)

Table 26. HIV patients only – changes in HIV viral load and CD4 cell count

Parameter	Standard Arm	Shortened arm
HIV viral load (<20 copies)	N (%)	N (%)
Screening		
Baseline		
Week 4		
SVR12		
Change in CD4 cell count	Mean (SD)	Mean (SD)
Screening		
Baseline		
SVR12		

Table 27. Listing of HIV patients with VL > 200 copies at any timepoint, by treatment arm

Study Arm	Study ID	Week first VL >200 copies/mL
Standard		
Shortened		

Table 28. Grading of severity of laboratory measures

Laboratory evaluation	Standard Arm (N=XX)	Shortened Arm (N=XX)
Haematological parameters		
Baseline Hb, g/L (mean, SD)		
Change in Hb at post-treatment week 12, g/L (mean, SD)		
Haemoglobin #, n (%)		
Grade 2		
Grade 3		
Grade 4		
Biochemical parameters		
Baseline ALT, U/L (mean, SD)		
ALT, n (%)		
Grade 2 (3-5x ULN)		
Grade ≥3 (>5x ULN)		
Change in ALT at post-treatment week 12, g/L (mean, SD)		
Baseline AST, U/L (mean, SD)		
AST, n (%)		
Grade 2 (3-5x ULN)		
Grade ≥3 (>5x ULN)		
Change in AST at post-treatment week 12, g/L (mean, SD)		
Baseline total bilirubin, mg/dl or mmol/L (mean, SD)		
Total bilirubin *, n (%)		
>2.5-3.0 mg/dl (43 – 51 mmol/L)		
>3.0 mg/dl (>51 mmol/L)		
Change in bilirubin at post-treatment week 12, g/L (mean, SD)		

At any time during treatment and up to 30 days post; each participant should only be included once - record most severe grade of anaemia for each participant

*At any time during treatment and up to 30 days post; add footnote, if bilirubin elevated at screening/baseline
